6.2 Participant Exclusion Criteria

- 1. Disease progression on either a first-line or the second-line platinum for metastatic PDAC or acinar cell carcinoma.
- 2. Patients with a second (or more) primary cancer, EXCEPTIONS: adequately treated nonmelanoma skin cancer, curatively treated in-situ cancer of the cervix, Ductal Carcinoma in Situ (DCIS), stage 1 cancers or low grade lymphomas curatively treated, without evidence of disease, and not requiring any active treatment prior to study entry, are eligible.
- 3. Resting EKG with QTC ≥ 450 msec detected on 2 or more time points within a 24-hour period or family history of long QT syndrome. If EKG demonstrates QTC ≥ 450 msec, patient will only be eligible if repeat EKG demonstrates QTC ≤ 450 msec. Fridericia QTc is acceptable for eligibility.
- 4. Patients with myelodysplastic syndrome/acute myeloid leukaemia or with features suggestive of MDS/AML.
- 5. Previous allogeneic bone marrow transplant.
- 6. Patients with symptomatic uncontrolled brain metastases. A scan to confirm the absence of brain metastases is not required for eligibility. The patient can receive a stable dose of corticosteroids before and during the study as long as the steroids were started at least 4 weeks prior to treatment and the steroid dose is ≤ 10 mg/day. Patients with spinal cord

Confidential

compression unless considered to have received definitive treatment for this and evidence of clinically stable disease for 28 days.

- 7. Patients unable to swallow orally administered medication and patients with gastrointestinal disorders likely to interfere with absorption of the study medication.
- 8. A diagnosis of immunodeficiency or is receiving chronic systemic steroid therapy (in dosing exceeding 10 mg daily of prednisone equivalent) or any other form of immunosuppressive therapy within 7 days prior to the first dose of study drug.
- 9. Immunocompromised patients, e.g., patients who are known to be serologically positive for human immunodeficiency virus (HIV).
- 10. Patients with known active hepatitis (i.e. Hepatitis B or C).
- a. Active hepatitis B virus (HBV) is defined by a known positive HBV surface antigen (HBsAg) result. Patients with a past or resolved HBV infection (defined as the presence of hepatitis B core antibody and absence of HBsAg) are eligible.
- b. Patients positive for hepatitis C virus (HCV) antibody are eligible only if polymerase chain reaction is negative for HCV RNA.
- c. Has a known history of active TB (Bacillus tuberculosis).
- 11. Any prior treatment with any PARP inhibitor, including olaparib.
- Any previous treatment with any anti-PD-1, anti-PD-L1, or anti-PD-L2 agent.
- 13. Has received systemic therapy 2 weeks prior to starting treatment
- 14. Patients with any recent investigational agents are not eligible unless at least 2 weeks or 5 half-lives of investigational agent prior to the first dose of study treatment have passed.
- 15. Live vaccines within 30 days prior to the first dose of study treatment and while participating in the study are not permitted. Examples of live vaccines include, but are not limited to, the following: measles, mumps, rubella, varicella/zoster, yellow fever, rabies, BCG, and typhoid vaccine. Seasonal influenza vaccines for injection are generally killed virus vaccines and are allowed; however, intranasal influenza vaccines (e.g., FluMist®) are live attenuated vaccines and are not allowed.
- 16. Active autoimmune disease that has required systemic treatment in the past 2 years is not permitted (i.e. with use of disease modifying agents, corticosteroids or immunosuppressive drugs). Replacement therapy (e.g., thyroxine, insulin, or physiologic corticosteroid replacement therapy for adrenal or pituitary insufficiency, etc.) is not considered a form of systemic treatment.
- 17. Palliative radiotherapy must have been completed 14 or more days before Cycle 1 Day 1.

- 18. If participant received major surgery within 4 weeks before screening, they must have recovered adequately from the toxicity and/or complications from the intervention prior to starting study treatment.
- 19. Participants must have recovered from all AEs due to previous therapies to ≤Grade 1 or baseline. Participants with ≤Grade 2 neuropathy may be eligible. Participants with ≤Grade 2 alopecia may be eligible as well.
- 20. Concomitant use of known strong CYP3A inhibitors (e.g. itraconazole, telithromycin, clarithromycin, protease inhibitors boosted with ritonavir or cobicistat, indinavir, saquinavir, nelfinavir, boceprevir, telaprevir) or moderate CYP3A inhibitors (e.g. ciprofloxacin, erythromycin, diltiazem, fluconazole, verapamil). The required washout period prior to starting is 2 weeks.
- 21. Concomitant use of known strong (e.g. phenobarbital, enzalutamide, phenytoin, rifampicin, rifabutin, rifapentine, carbamazepine, nevirapine and St John's Wort) or moderate CYP3A inducers (e.g. bosentan, efavirenz, modafinil). The required washout period prior to starting is 5 weeks for enzalutamide or phenobarbital and 3 weeks for other agents.

7.0 RECRUITMENT PLAN

All participants meeting the eligibility requirements will be considered for enrollment regardless of sex, race, or religion. Subjects will be accrued from the Solid Tumor Gastrointestinal Oncology Service (STGI). Eligibility criteria may not be waived by the investigator. Discussions regarding protocol enrollment and participant eligibility will begin with any of the investigators named on the consenting professionals list. Participants will be made aware of the protocol, its specific aims and objectives, and the potential risks and benefits the subjects may incur. Participants will be required to read, agree to, and sign an institutional review board (IRB)-approved informed consent form prior to registration for this trial. Participants will be consented prior to screening activities and treatment initiation. Our target accrual is minimum 47 (Cohort A: 18, B: 15, C: 15) to maximum 63 eligible patients. Approximately 800 patients with PDAC are seen at MSK annaully. About 125 patients have HRD who are expected to meet the genetic eligibility criteria for Cohort A and B and about 50-75 for Cohort C each year. Based on our experience with previous trials of this type, we expect an accrual time of approximately 2.5-3 years.

7.1 Research Participant Registration

Confirm eligibility as defined in the section entitled Inclusion/Exclusion Criteria. Obtain informed consent, by following procedures defined in section entitled Informed Consent Procedures. During the registration process registering patients will be required to complete a protocol specific Eligibility Checklist. The patients signing the Eligibility Checklist is confirming whether the participant is eligible to enroll in the study. Study staff are responsible for ensuring that all institutional requirements necessary to enroll a participant to the study have been

completed. See related Clinical Research Policy and Procedure #401 (Protocol Participant Registration).

7.2 Randomization

This study is an open-label, non-randomized, genomic biomarker-enriched study. Patients are allocated to the 3 cohorts based on genomic profile and platinum sensitivity.

8.0 INFORMED CONSENT PROCEDURES

Before protocol-specified procedures are carried out, consenting professionals will explain full details of the protocol and study procedures as well as the risks involved to participants prior to their inclusion in the study. Participants will also be informed that they are free to withdraw from the study at any time. All participants must sign an IRB/PB-approved consent form indicating their consent to participate. This consent form meets the requirements of the Code of Federal Regulations and the Institutional Review Board/Privacy Board of this Center. The consent form will include the following:

- 1. The nature and objectives, potential risks and benefits of the intended study.
- 2. The length of study and the likely follow-up required.
- 3. Alternatives to the proposed study. (This will include available standard and investigational therapies. In addition, patients will be offered an option of supportive care for therapeutic studies.)
- 4. The name of the investigator(s) responsible for the protocol.
- 5. The right of the participant to accept or refuse study interventions/interactions and to withdraw from participation at any time.
- 6. The voluntary consent for #12-245 and #06-107 outside of this trial which will allow identification of which group the patient was treated under and future biospecimen use for research. The consent will also allow adjacent normal tissue near cancerous tissue to be collected for research analysis.

Before any protocol-specific procedures can be carried out, the consenting professional will fully explain the aspects of patient privacy concerning research specific information. In addition to signing the IRB Informed Consent, all patients must agree to the Research Authorization component of the informed consent form.

Each participant and consenting professional will sign the consent form. The participant must receive a copy of the signed informed consent form.

9.0 PRE-TREATMENT/INTERVENTION

 Prior to treatment initiation, all subjects will undergo the following procedures: Separate cross-sectional imaging: CT chest/abdomen/pelvis with contrast or MRI abdomen/pelvis and chest CT without contrast (if IV contrast is contraindicated) within 4 weeks of planned first date of POLAR treatment. Separate CT scans of the chest, abdomen, and pelvis are acceptable, provided they are done 4 weeks of the first treatment.

Research Blood Draws

All collected blood samples at MSK will be processed by the following protocol:

In addition, the following evaluations will be required at the times indicated in Section 11.1 Adverse Event (AE) Monitoring Table 10.

Table 1. Standard-of-care and research blood draws

Standard-of-care labs	 Hematology: complete blood count (CBC), including red blood cell (RBC) count, Hgb, hematocrit, platelet count, and WBC count with differential (neutrophils, eosinophils, lymphocytes, monocytes, basophils, and other cells) Chemistry panel (serum or plasma): sodium, potassium, chloride, bicarbonate, blood urea nitrogen (BUN) or urea, creatinine, glucose, calcium, magnesium, phosphorus, total bilirubin, ALT, AST, alkaline phosphatase, lactate dehydrogenase (LDH), total protein, albumin, amylase, and lipase Coagulation: prothrombin time (PT), activated partial thromboplastin time (aPTT), and international normalized ratio (INR) Pregnancy test: All women of childbearing potential (including those who have had a tubal ligation). If a urine pregnancy test result is positive, dosing will be delayed until the patient's status is determined by a serum pregnancy test and it is confirmed that the result is not a false positive due to HCG tumor secretion. The pregnancy test should be during screening within 28 days prior to the start of study treatment. Urinalysis: dipstick (pH, specific gravity, glucose, protein, ketones, blood) and microscopic examination (sediment, RBCs, WBCs, casts, crystals, epithelial cells, bacteria) if warranted by dipstick results Thyroid function testing: thyroid-stimulating hormone (TSH), free T3, and free T4 C-reactive protein (CRP) Serology: (Only if these were not performed at MSK) Hepatitis B surface antigen (HBsAg), antibodies against HBsAg, and hepatitis B core antibody (HCV). HCV RNA test is required prior total hepatitis B core antibody (anti-HBc) Anti-hepatitis C virus antibody (HCV). HCV RNA test is required prior to Cycle 1, Day 1 for consideration of eligibility if the patient has positive serology for anti-HCV HIV antibodies
Research blood	 Blood is stored at 20-25°C up to 4 hours before processing Phosphate-buffered saline (PBS) is added to blood samples to achieve a total volume of 50 mL

- 2
- 15 mL of Ficoll-Paque PLUS is added to the blood samples
- Samples are centrifuged at 1000g for 20 minutes at 21°C
- The layer containing PBMCs is harvested
- BEAD solution containing 500 mL of PBS and 5 mL of fetal bovine serum is added to the PBMCs to achieve a final volume of 50 mL
- Samples are centrifuged at 650g for 5 minutes at 4°C, and the supernatant is discarded
- 1-2 mL of BEAD is added to the remaining PBMCs, and samples are centrifuged at 250g for 10 minutes at 4°C
- The supernatant is discarded, and cells are resuspended in freezing media containing 90% fetal bovine serum and 10% dimethyl sulfoxide
- Cells are frozen in a -80°C freezer for 24 hours and then transferred to liquid nitrogen for long-term storage
- Epstein-Barr nuclear antigen (EBNA) IgG Cytomegalovirus (CMV) IgG

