- Variants of unknown significance (VUS) or benign polymorphisms of above 17 HR-genes from Cohort A and B are considered non-pathogenic and will be excluded from cohort A or B. However, if the participant demonstrates platinum sensitivity, patient can be considered eligible for Cohort C.
- 3. A recurrence after curative surgery is eligible if the recurrence is > 6 months after the last date of adjuvant therapy and the participant has at least stable or responding disease on platinum therapy and meet the above genomic or platinum sensitivity criteria.
- Eastern Cooperative Oncology Group (ECOG) performance status 0-2 (Appendix 1: ECOG)
- 5. Patients must have normal organ and bone marrow function measured within 28 days prior to administration of study treatment as defined as below:
 - Absolute neutrophil count (ANC) ≥1500/µL
 - Hemoglobin ≥9.0 g/dL or ≥5.6 mmol/La
 - Platelets ≥100 000/µL

POLAR: a phase 2 trial for pembrolizumab and olaparib maintenance for metastatic PDAC and HRD and/or Exceptional Response to Platinum – Ver. 5/3/2020

•

2

- Total bilirubin ≤ 2 x ULN
- AST (SGOT) and ALT (SGPT) ≤2.5 × ULN (≤5 × ULN for if liver metastases)
- Creatinine ≤2 x ULN
- 6. Patients with measurable disease and/or non-measurable or no evidence of disease assessed at baseline by CT (or MRI where CT is contraindicated) are eligible.
- 7. Postmenopausal or evidence of non-childbearing status for women of childbearing potential: negative urine or serum pregnancy test. Postmenopausal is defined as:
 - Amenorrhoeic for 1 year or more following cessation of exogenous hormonal treatments
 - Luteinizing hormone (LH) and Follicle stimulating hormone (FSH) levels in the postmenopausal range for women under 50
 - Radiation-induced oophorectomy with last menses >1 year ago
 - Chemotherapy-induced menopause with >1-year interval since last menses
 - Surgical sterilization (bilateral oophorectomy or hysterectomy)

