10.0 TREATMENT/INTERVENTION PLAN

10.1 Administration

Within 4 weeks of screening date, eligible patients will receive combination pembrolizumab and olaparib as maintenance therapy until clinical or radiographic progression or discontinuation due to -limiting toxicity. If a patient requires discontinuation of either olaparib or pembrolizumab for reasons of toxicity and if in the opinion of the treating MD the patient is continuing to derive benefit, the patient is able to continue on study. Additionally, in the absence of unacceptable toxicity, participants who meet criteria for disease progression per RECIST 1.1 while receiving treatment will be permitted to continue treatment, if in the opinion of the treating MD the patient is continuing to derive benefit from the treatment. iRECIST will be used to evaluate the objective response rate and the co-primary endpoint of overall response rate will be assessed by RECIST v1.1. (Section 12.0 CRITERIA FOR REMOVAL FROM STUDY).

The POLAR treatment will be administered to subjects as outlined in Figure 1 - Schematic treatment and biospecimen collection schedule. Approximately within 4 weeks of screen visit, patient will get baseline biopsy and will start the first dose pembrolizumab 200 mg IV every 3 weeks and olaparib 300 mg twice daily orally. After the first 6 months (9 cycles), on C10D1 Pembrolizumab 400 mg IV every 6 week plus olaparib 300 mg twice a day orally will be continued. Per treating investigator's discretion, patients may remain at Pembrolizumab 200 mg IV every 3 weeks after the first 9 cycles. Additionally, to accomodate patients traveling far distances, if, per treating investigator, after the first or second imaging, there are no toxicities, patient's dosing of Pembrolizumab may change to 400 mg IV every 6 weeks. All cycles will be 21 days (3 weeks) in length. Subjects will be monitored for toxicity every three weeks for the first 9 cycles, and every six weeks thereafter, unless clinically indicated to be monitored every 3 weeks.

Table 2. Trial treatment (POLAR)

Drug	Dose	Dose Frequency	Route of Administration	Treatment Period	Use
Pembrolizumab	200 mg	Q3W	IV infusion	Day 1 of each 3- week cycle for cycle 1-9	experimental
Pembrolizumab	400mg	Q6W	IV infusion	Day 1 of every even cycle beginning with Cycle 10	experimental
Olaparib	300 mg (two 150 mg)	BID	Orally	Daily continuously	experimental

The following parameters must be acceptable prior to initiation of protocol treatment:

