Treatment Cycle/Title:	Pre- screening (Visit 1)	1	2	3	4	5	6	7	8	9	Even Cycles (ex. 10, 12, 14 etc.)	Odd Cycles (ex. 11, 13, 15, etc.)	Discontinua tion	Safety Follow-up (in clinic)	Survival Follow- Up (Clinic or phone)
Scheduling Window (Days):	-28		± 3	± 3	±3	At time of Discontinua tion	30 days and 60 days post discontinuation	Every 12 weeks for 5 years							
Directed Physical Examination	Х	x	х	х	Х	х	x	x	x	х	х		Х		
Vital Signs and Weight	Х	х	х	Х	х	х	х	х	х	Х	Х		Х	Х	
ECOG Performance Status	Х	х	х	Х	Х	х	х	Х	х	х	х		Х		
Laboratory Procedure	s/Assessment	s: an	alysi	is per	form	ned b	y LO	CAL	labor	atory					
Pregnancy Test – Urine or Serum □- HCG	Х	х													
PT/INR and aPTT	Х												Х		
CBC with Differential	Х	Х	х	Х	х	х	х	х	Х	Х	Х		Х		
Comprehensive Serum Chemistry Panel	Х	х	х	Х	х	х	х	х	х	Х	Х		х		
CA 19-9, CEA	Х	Х	Х	Х	Х	Х	Х	Х	Х	Х	Х		Х		
HBsAg, IgG anti- HBs, Anti-HCV, HIV screen	х														

Trial Period:	Screening Phase		Trea	itmen	ıt Cy	cles	(21 D	ay C	ycles)	Pembro Q6 Wk		End of Treatment	Post-Treatment	
Treatment Cycle/Title:	Pre- screening (Visit 1)	1	2	3	4	5	6	7	8	9	Even Cycles (ex. 10, 12, 14 etc.)	Odd Cycles (ex. 11, 13, 15, etc.)	Discontinua tion	Safety Follow-up (in clinic)	Survival Follow- Up (Clinic or phone)
Scheduling Window (Days):	-28		± 3	± 3	± 3	At time of Discontinua tion	30 days and 60 days post discontinuation	Every 12 weeks for 5 years							
Urinalysis	Х			Х			Х			Х	Х				
FT3, FT4 and TSH	Х			Х			Х			Х	Х				
EKG	Х			Х			Х			Х	Х				
Efficacy Measurement	s														
Tumor Imaging*	Х				Х			Х			>	(*	Х		
Tumor Biopsies/Archi	Tumor Biopsies/Archival Tissue Collection/Correlative Studies Blood														
Biopsy ^{1, 2, 3}	Х			Х									Х		
Correlative Studies Blood Collection ⁴	Х			Х			Х				>	⟨⁴	Х		
Blood draw to generate plasma for cell free (cf)DNA analysis ⁵	Х			Х			Х				>	〈 5	Х		

Trial Period:	Screening Phase	Treatment Cycles (21 Day Cycles)									Pembro	Q6 Wk	End of Treatment	Post-Treatment	
Treatment Cycle/Title:	Pre- screening (Visit 1)	1	2	3	4	5	6	7	8	9	Even Cycles (ex. 10, 12, 14 etc.)	Odd Cycles (ex. 11, 13, 15, etc.)	Discontinua tion	Safety Follow-up (in clinic)	Survival Follow- Up (Clinic or phone)
Scheduling Window (Days):	-28		± 3	± 3	±3	At time of Discontinua tion	30 days and 60 days post discontinuation	Every 12 weeks for 5 years							

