12.0 CRITERIA FOR REMOVAL FROM STUDY

- **12.1. Disease Progression:** Patients with confirmed progressive disease following POLAR treatment will be removed from treatment, their disease pathologically documented, and the patient will be followed for survival and the immunologic endpoints. However, in the absence of unacceptable toxicity, participants who meet criteria for disease progression per RECIST 1.1 while receiving treatment will be permitted to continue treatment if in the opinion of the treating MD the patient is continuing to derive benefit from the treatment. iRECIST will be used to evaluate the response and the co-primary endpoint of overall response rate will be assessed both by RECIST and iRECIST.
- **12.2 Extraordinary Medical Circumstances:** If at any time the constraints of this protocol are detrimental to the patient's health, the patient shall be withdrawn from treatment. In this event:
 - 12.2.1. Document reasons for withdrawal and record whether this action was patient or physician directed.
 - 12.2.2. The patient will remain technically on-study although treatment has been discontinued. The patients will be followed for relapse and survival.

12.3. Unexpected or Life-Threatening Toxicity (CTCAE v5.0 Table):

- 12.3.1. Direct questions regarding drug therapy to the Principal Investigator.
- 12.3.2. Reporting requirements and procedures depend upon:
 - (1) whether agents are suspected of causing toxicity, (2) whether possibility of such toxicity was reported in the consent form, or manufacturer's literature (Published Toxicity), (3) the severity or grade of the toxicity.
- 12.3.3. Expected toxicities:
- 12.3.3.1. Grade 4 myelosuppression: Report only as part of regular data submission.
- 12.3.3.2. All other toxicities, Grades 4: Written Report to Principal and Co-Investigators, within 10 working days.
- 12.3.3.3. All other toxicities, Grades 1 to 3: Report only as part of regular data submission.
- 12.3.4. Unexpected Toxicities: Unexpected toxicities are toxicities that are not listed in the toxicity management section of the protocol, the consent form, or the manufacturer's package inserts. All unexpected toxicities will be reported to Principal and Co-Investigators, within 10 working days.
- 12.4. Patient noncompliance with the protocol requirements
- 12.5. Patient request to withdraw
- 12.6. Development of serious intercurrent illness during treatment
- 12.7. Patient removed at the discretion of the PI

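### Table 1's dosing hold after a positive urine pregnancy test states a release condition that a confirmed pregnancy satisfies

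*Protocol*

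**What the plan says.** Section 9.0, Table 1, sets a hold for women of childbearing potential. After a positive urine test, "dosing will be delayed until the patient's status is determined by a serum pregnancy test" and, joined by a plain conjunction, "it is confirmed that the result is not a false positive due to HCG tumor secretion". The sentence says nothing about what follows if pregnancy is confirmed.

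The other places that bear on it are:

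- Section 6.1, inclusion criterion 7, asks for a "negative urine or serum pregnancy test". It gives no time window of its own for that test.
- Section 7.0: "Eligibility criteria may not be waived by the investigator".
- Section 10.1: "eligible patients will receive combination pembrolizumab and olaparib as maintenance therapy".
- Section 9.0 says that "the following evaluations will be required at the times indicated in Section 11.1". The schedule there is Table 9, whose row "Pregnancy Test – Urine or Serum" is marked at Pre-screening and at Cycle 1.
- Section 15.0 covers only the reporting of pregnancies, not dosing.

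**The concern.** A hold that ends when conditions are met should end only in the cases where treatment is acceptable. Here the second condition carries its negation on the wrong side. Proving that a positive result does not come from tumor HCG makes pregnancy more likely, yet that proof is what lifts the hold.

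What is at stake is participant safety and the clarity of a written instruction at the first dose. Site staff who look up what to do after a positive test will find this sentence, and it does not tell them to stop if the patient is pregnant.

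**Working it through.** No figure is involved, so the check is a reading of the rule case by case, followed by the point in the schedule at which each case can arise.

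**Step 1: the release rule.** The hold ends when A and B both hold.

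- A: a serum test has determined the patient's status.
- B: it is confirmed that the result is not a tumor-HCG false positive.

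| Case after a positive urine test | A | B | Hold under Table 1 | Assessment |
|---|---|---|---|---|
| Pregnancy confirmed by serum | met | met | ends | wrong |
| Serum negative, urine positive not due to tumor HCG | met | met | ends | correct |
| Positive due to tumor HCG | met | cannot be met | never ends | agrees with inclusion criterion 7 if urine and serum are both positive |

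Taking the word result to mean the urine result or the serum result does not change the first or third row.

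**Step 2: positive at screening.** A pregnant patient has no negative test to offer, so she fails inclusion criterion 7. Section 7.0 forbids a waiver and Section 10.1 gives drug to eligible patients only. The faulty sentence has no effect on the outcome.

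**Step 3: negative at screening, positive at Cycle 1.** Table 9 marks the pregnancy test at Pre-screening and Cycle 1, but marks the inclusion and exclusion review at Pre-screening only. This patient has already passed inclusion criterion 7 on her screening test. Four places deal with pregnancy or its testing: inclusion criterion 7, Table 1, Table 9 and Section 15.0. Only Table 1 says what happens to dosing after a positive test. The eligibility rules can still be read as protecting her, but by inference, while the explicit instruction lets the hold end.

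The layout of Table 9 is imperfect in the text available, so the column positions in this step carry some caution.

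**Step 4: the rule with the condition changed to exclusion of pregnancy.** The first case stays on hold and the second is released. In the third, the hold can end once pregnancy is excluded, and inclusion criterion 7 continues to decide eligibility.

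**The case against.** The strongest reply is that the sentence only sets how long dosing waits for a serum work-up. It lifts a delay and does not authorise treatment. Eligibility is decided elsewhere, cannot be waived, and requires a negative test. Section 12.2 adds that "If at any time the constraints of this protocol are detrimental to the patient's health, the patient shall be withdrawn from treatment", and Section 12.7 allows removal at the principal investigator's discretion. Any clinician would read the intended sense. Most of this stands, and it is why the point is of low severity. It does not make the sentence right, and it is weakest for a positive test at Cycle 1, after the marked eligibility review.

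Stronger readings are tempting, and the documents do not support them:

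- A reader might infer that the protocol permits a pregnant patient to be dosed. It does not: ending a hold is not permission, and the eligibility rules remain in force.
- A reader might say that the rule does the opposite of its purpose throughout. The case of a positive urine test with a negative serum test works as it should.
- A reader might see an equal fault in the tumor-HCG case, where the hold never ends. With both tests positive, Table 1 and inclusion criterion 7 both withhold drug, so they agree, and nothing in the protocol says that such patients were meant to be treated.
- A reader might point to the absence of pregnancy from the exclusion, pre-treatment and removal lists. That is weak evidence, because the protocol handles pregnancy through an inclusion criterion and the pre-treatment list contains only blood-count and chemistry limits.

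**Conclusion.** The point holds as an error of wording in a safety instruction: the release condition in Table 1 is one that a confirmed pregnancy meets, and the sentence does not bar dosing in that case. Severity is low. At screening the error is harmless because inclusion criterion 7 decides. It has practical weight mainly for a positive urine test at Cycle 1 after a negative screening test.

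The conclusion that the wording is wrong rests only on the sentence itself. The conclusion about where it matters also rests on reading Table 9 as marking the test at Cycle 1 and eligibility review at Pre-screening only. The documents do not show that any pregnant patient would be treated, and no number of affected patients can be derived from them. Sample size, type I error, power, endpoints and analyses are untouched.

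**What to change.** Replace the hold in Table 1 with:

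*After a positive urine pregnancy test, dosing will be withheld until pregnancy has been excluded; a patient with confirmed pregnancy will not receive study treatment. Ending this hold does not replace inclusion criterion 7.*

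The last sentence is needed. Without it, a patient with tumor HCG would be released by Table 1 once pregnancy is excluded while still failing inclusion criterion 7, a mismatch that the current text does not have. If the clinical team wishes to treat such patients, that requires an exception in inclusion criterion 7 and should be decided separately.

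The cost is a short edit to one table entry at the next amendment. Eligibility, tests, visits and analyses stay as they are.
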